12.5 Handling of Missing Data

Guidelines promulgated in the National Research Council report on handling of missing data will be followed^{28,29}.

13.0 RISK/BENEFIT ASSESSMENT

13.1 Known Potential Benefits to the Subjects

Possible benefits of participating in this research study include improved postoperative analgesia, decreased opioid requirements and related side effects, shorter intensive care unit and hospital length of stay, and a decreased risk of developing chronic pain related to the surgery.

13.2 Known Potential Risks

PIFB risks

Possible risks of a pecto-intercostal fascial plane block include bleeding, infection, failed block, vascular injury, or pneumothorax³⁰. However, compared to the transversus thoracic muscle plane block, the PIFB is more superficial and thought to be safer due to the increased distance between the fascial plane and the pleura and internal thoracic vessels³¹. No serious block related complications have been reported with the

PIFB^{19,20}. Reactions to bupivacaine are characteristic of those associated with other amide-type local anesthetics. A major cause of adverse reactions in this group of drugs is related to excessive plasma levels due to overdosage, unintentional intravascular injection or slow metabolic degradation. Central nervous system reactions as a result of these may include restlessness, anxiety, dizziness, tinnitus, blurred vision, or tremors may occur, possibly proceeding to convulsions, drowsiness, unconsciousness and respiratory arrest. Other central nervous system effects may be nausea, vomiting, chills, and constriction of the pupils. The incidence of convulsions associated with the use of local anesthetics varies with the procedure used and the total dose administered. Cardiovascular system reactions from high doses or unintentional intravascular injection may lead to high plasma levels and related depression of the myocardium, decreased cardiac output, heartblock, hypotension, bradycardia, ventricular arrhythmias, including ventricular tachycardia and ventricular fibrillation, and cardiac arrest. Allergic-type reactions are rare and may occur as a result of sensitivity to the local anesthetic or to other formulation ingredients, such as the antimicrobial preservative methylparaben contained in multiple-dose vials or sulfites in epinephrine-containing solutions. These reactions are characterized by signs such as urticaria, pruritus, erythema, angioneurotic edema (including laryngeal edema), tachycardia, sneezing, nausea, vomiting, dizziness, syncope, excessive sweating, elevated temperature, and possibly, anaphylactoid-like symptomatology (including severe hypotension). Neurologic effects following procedures may include persistent anesthesia, paresthesia, weakness, paralysis, all of which may have slow, incomplete, or no recovery.

In clinical trials utilized for FDA approval of Exparel (liposomal bupivacaine), the most common adverse reactions (incidence greater than or equal to 10%) following EXPAREL administration were nausea, constipation, and vomiting. The common adverse reactions (incidence greater than or equal to 2% to less than 10%) following EXPAREL administration were pyrexia, dizziness, edema peripheral, anemia, hypotension, pruritus, tachycardia, headache, insomnia, anemia postoperative, muscle spasms, hemorrhagic anemia, back pain, somnolence, and procedural pain. The less common/rare adverse reactions (incidence less than 2%) following EXPAREL administration were chills, erythema, bradycardia, anxiety, urinary retention, pain, edema, tremor, dizziness postural, paresthesia, syncope, incision site edema, procedural hypertension, procedural hypotension, procedural nausea, muscular weakness, neck pain, pruritus generalized, rash pruritic, hyperhidrosis, cold sweat, urticaria, bradycardia, palpitations, sinus bradycardia, supraventricular extrasystoles, ventricular extrasystoles, ventricular tachycardia, hypertension, pallor, anxiety, confusional state, depression, agitation, restlessness, hypoxia, laryngospasm, apnea, respiratory depression, respiratory failure, body temperature increased, blood pressure increased, blood pressure decreased, oxygen saturation decreased, urinary incontinence, vision blurred, tinnitus, drug hypersensitivity, and hypersensitivity.

Risks associated with loss of confidentiality

There is a risk that information recorded about subjects will be shared with people who would not normally have access to this information.

Unknown risks

This study may involve risks to the subject which are currently unforeseeable. We will inform subjects as soon as possible if we discover any information that may affect the subject's health, welfare, or decision to be in this study.

13.3 Risk/Benefit Analysis

PIFB:

The risk of infection will be minimized by using the standard of care for regional anesthesia including a mask and sterile gloves for the provider, sterilizing the field of the block, and using sterile equipment. The

risk of bleeding will be minimized by adhering to the American Society of Regional Anesthesia evidenced-based guidelines for regional anesthesia in the patient receiving antithrombotic or thrombolytic therapy³². Despite not being a neuraxial technique, we will use the more conservative guidelines specific for neuraxial techniques to further minimize the risk of significant bleeding. Performing the procedure under ultrasound guidance allows us to identify all important adjacent structures to avoid injury to surrounding tissues and blood vessels.

Blinding:

All of the patients enrolled in the study will receive wrist bands indicating the possible use of liposomal bupivacaine in order to avoid the use of any additional local anesthetic or regional intervention for 96 hours. To minimize the risk associated with blinding, the co-principal investigators will be available to be contacted by other caregivers for unblinding in the situation where that becomes necessary for patient safety.

Failed block:

The risk of a failed block and inadequate analgesia will be minimized by the availability of supplemental oral and intravenous analgesics.

In light of the mitigation strategies described above we believe the risk-to-benefit ratio is acceptable.

14.0 DATA AND SAFETY MONITORING

14.1 Adverse Event (AE) Definition

An adverse event (AE) is defined as any untoward or unfavorable medical occurrence in a human subject enrolled in this study, including any abnormal sign, symptom, or disease temporally associated with the PIFB or other study procedure that appears or worsens during the study or study follow-up period. AEs may be anticipated (i.e. redness or soreness at the injection site) or unanticipated (i.e. bleeding, infection, allergic reaction). Adverse event information will be collected throughout the entire study, and through resolution of the AE if present.

Study staff will monitor for AEs by following up with the patient on post-operative day (POD) 1 and POD 90, electronic chart review, and with additional follow-up as needed related to any concerns for AEs from the primary care teams. All AEs will be recorded on a study data sheet and in the electronic database by a study investigator or study staff. In the event of an unanticipated AE, the primary anesthesia or intensive care unit team caring for the subject will intervene as deemed appropriate.

14.2 Serious Adverse Event (SAE) Definition

A serious adverse event (SAE) is defined as any adverse event that meets one of the following criteria:

- Results in death
- Is life-threatening
- Requires hospitalization or prolongs existing hospitalization
- Results in significant or persistent disability or incapacity
- Results in a congenital anomaly/birth defect

14.3 Classification of an Adverse Event

14.3.1 Severity of Event

The severity of all adverse events will be assessed according to the following scale:

- Mild: not requiring treatment or intervention
- Moderate: resolved with treatment/intervention
- Severe: inability to carry on normal activities and required professional medical attention

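### The adverse event severity grades in 14.3.1 rest on three different criteria and are neither mutually exclusive nor exhaustive

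*Combined protocol and SAP*

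**What the plan says.** Section 14.3.1 applies to every event: "The severity of all adverse events will be assessed according to the following scale". The three levels are:

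- "Mild: not requiring treatment or intervention"
- "Moderate: resolved with treatment/intervention"
- "Severe: inability to carry on normal activities and required professional medical attention"

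The section gives no order of precedence and no instruction for an event that fits two levels or none.

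Other sections bear on how the grade is used:

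- Section 14.2 defines seriousness separately, including life-threatening events and lasting disability.
- Section 14.4 ties immediate notification and the enrollment halt to seriousness. It records non-serious events from the start of the study procedure until hospital discharge.
- Section 14.5 makes unexpected severity one of the ways in which an event can count as an unanticipated problem.
- Section 12.4 specifies no analysis by severity grade.

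Section 13.2 names the risks to which the scale would be applied. They include central nervous system reactions "possibly proceeding to convulsions, drowsiness, unconsciousness and respiratory arrest" and nausea, constipation and vomiting at an incidence of 10% or more after the liposomal product.

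**The concern.** A severity scale should place each event on exactly one step of one ordered dimension. Here the steps measure different things: whether treatment was needed, whether it worked, and how the patient functioned and was attended. Such steps need not be ordered, can overlap, and can leave gaps.

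Two further problems follow from the wording:

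- **Timing.** Moderate depends on resolution, so it cannot be assigned until the event has ended.
- **Setting.** Non-serious events are collected only up to discharge. Over much of that time a patient recovering from sternotomy cannot carry on normal activities and is already under professional care. Unless it is judged against the expected postoperative course, the Severe wording separates little.

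At stake is the consistency of a required field. Two assessors following the text could grade one event differently, and some events would have no valid grade. Severity and relationship to the study are the only two classifications that 14.3 prescribes for an adverse event.

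**Working it through.** The plan states no figure on this point, so there is none to reproduce. The check is to apply the definitions literally and count what they return.

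**Inputs (14.3.1).** Four yes/no attributes of an event:

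- T: treatment required
- R: resolved
- I: unable to carry on normal activities
- P: professional medical attention required

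**Definitions as written**

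- Mild = not T
- Moderate = T and R
- Severe = I and P

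**Case A: treatment implies medical attention and the reverse (P = T).** There are 2 × 2 × 2 = 8 patterns.

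| T | R | I | Grade(s) met |
|---|---|---|---|
| no | no | no | Mild |
| no | no | yes | Mild |
| no | yes | no | Mild |
| no | yes | yes | Mild |
| yes | no | no | none |
| yes | no | yes | Severe |
| yes | yes | no | Moderate |
| yes | yes | yes | Moderate and Severe |

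Six patterns give one grade, one gives two and one gives none: 6 + 1 + 1 = 8.

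**Case B: P free to differ from T.** There are 16 patterns.

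- T = no (8 patterns): all are Mild. The 2 with I and P both present are also Severe. Result: 6 with one grade, 2 with two.
- T = yes, R = yes (4 patterns): all are Moderate. The 1 with I and P both present is also Severe. Result: 3 with one grade, 1 with two.
- T = yes, R = no (4 patterns): the 1 with I and P both present is Severe, and the others meet nothing. Result: 1 with one grade, 3 with none.

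Totals: one grade 6 + 3 + 1 = 10; two grades 2 + 1 = 3; no grade 3.

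**Applied to risks named in 13.2**

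- A convulsion that is treated and resolves, and that incapacitates the patient while it lasts: Moderate and Severe.
- Nausea that is treated, persists and does not incapacitate: no grade. If it then resolves, it becomes Moderate. If the assessor regards any patient in intensive care as unable to carry on normal activities, it is Severe as well.

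The second example shows that the problem reaches common, non-serious events as well as rare toxicities.

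**The case against.** The strongest reply is that little turns on the grade. A life-threatening or disabling event is serious under 14.2 whatever its grade, and 14.4 acts on seriousness. A cardiac arrest would lead to notification, the enrollment halt and a report to the IRB under either label. Section 12.4 plans no comparison by grade. Section 14.1 follows events to resolution, so a treated event that eventually resolves can be graded in the end. All of this stands and limits the consequence. It does not remove the point: 14.3.1 still requires a grade for every event, non-serious events have no seriousness pathway behind them, and 14.5 relies partly on a judgment of severity that only 14.3.1 defines.

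Three stronger readings are tempting, and the documents do not support them.

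1. *The scale grades a treated cardiac arrest or convulsion as Moderate.* Only Moderate refers to whether treatment worked. Such an event plausibly meets Severe too, so the text permits the lower grade but does not force it.
2. *Lasting numbness is wrongly graded Mild.* Section 13.2 does warn of "persistent anesthesia, paresthesia, weakness, paralysis, all of which may have slow, incomplete, or no recovery". But numbness that needs no treatment could properly be mild in intensity, and permanence is an outcome. A scale free of outcome could give the same grade. If the numbness amounted to significant or persistent disability, 14.2 would make it serious. The definition also speaks of treatment not being required, which differs from treatment not being given.
3. *A summary by severity would understate harm.* The direction is unclear. The Moderate wording can pull grades down, while the Severe wording, met by many inpatients, can pull them up.

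**Conclusion.** The point holds as a defect of definition with limited consequences. Followed as written, 14.3.1 gives two grades to a treated, resolved, incapacitating event and none to a treated, unresolved, non-incapacitating one. That is 2 of 8 attribute patterns under the simpler assumption and 6 of 16 under the wider one. These counts describe the logic of the scale. They are not error rates, because the documents do not say how often each pattern will occur.

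The likely effect is inconsistent or missing severity grades, mainly for non-serious events, and weaker support for the severity judgment in 14.5. Handling of serious events and the planned efficacy analyses are unaffected.

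The conclusion assumes a literal reading of the three definitions and that no grading guidance exists outside the documents. The case report form was not available, so treatment and outcome may already be recorded there.

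**What to change.** Reword 14.3.1 as follows:

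- Use one ordered intensity scale that makes no reference to outcome, with each level judged against the expected course after cardiac surgery.
- State that the highest applicable grade is assigned.
- Record treatment given and outcome (for example resolved, ongoing, or resolved with sequelae) as separate fields, if the case report form does not already do so.

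Separate life-threatening and fatal levels are optional, since 14.2 already captures those events.

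The cost is a change of wording and possibly two form fields. If enrollment has begun, events already recorded need regrading by assessors blinded to arm. Interventions, endpoints and sample size do not change.

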14.3.2 Relationship to Study, Study Procedure(s) and/or Study Intervention(s)

A co-principal investigator will determine the relationship of any adverse events to the research intervention using the following scale:

- Definite: AE is clearly related to the study procedures
- Probable: AE is likely related to the study procedures
- Possible: AE is possibly related to the study procedures
- Unlikely: AE is doubtfully related to the study procedures
- Unrelated: AE is clearly not related to the study procedures

14.4 Reporting AEs and SAEs

Non-serious adverse events will be recorded if they occur from the time the study procedure begins to the patient's hospital discharge. All serious adverse events will be recorded if they occur from the time that the subject provides informed consent through and including the 90-day follow-up phone call. All adverse events will be communicated to and between the co-principal investigators.

Given the minimal risk associated with the use of PIFB, no serious adverse events are anticipated. If a SAE occurs, the study co-principal investigators will be immediately notified and further enrollment in the study will be halted until a full explanation of the cause of the event and its relationship to the PIFB and/or study procedure is understood. The IRB will be notified and re-initiation of study enrollment will not occur until approved by the IRB.

14.5 Unanticipated Problems

An unanticipated problem (UP) is defined as an event that meets all of the following criteria:

- Unexpected in severity, nature, or frequency given the research procedures and the characteristics of the subject population
- Related or possibly related to participation in the research study:

The investigator will report UPs to the reviewing IRB and lead Principal Investigator (PI). The UP report will include the following information:

- Protocol identifying information: protocol title and number, PI's name, and the IRB project number;
- A detailed description of the event, incident, experience, or outcome;
- An explanation of the basis for determining that the event, incident, experience, or outcome represents an UP;
- A description of any changes to the protocol, informed consent documents, or other corrective actions that have been taken or are proposed in response to the UP.
- Report UPs within the timeframe(s) specified by the IRB(s) of record.

14.6 Other Reportable Events

Reporting timeframes begin when the site learns of the occurrence of the event.

Event	Definition	Reporting
-------	------------	-----------

Breach of confidentiality	The exposure of any study information or communications directly related to a study subject to anyone not named as study staff or the release of a study subject's identifiable information to study staff who were not specified to receive such information in the protocol or IRB application.	Treat as major deviation (below)
Protocol deviation	A deviation is an incident involving a departure from the IRB-approved protocol in the actual conduct of the study. Deviations may result from the action of the participant, investigator, or staff.	See below
Major deviations	Deviations are considered major when the unapproved change(s) in previously approved research activities, implemented without IRB approval, may potentially adversely affect subjects' rights, safety, welfare, or willingness to continue participation, or affect the scientific design of the study and/or the integrity of the resultant data.	Treat as an Unanticipated Problem (above)
Minor deviations	Deviations are considered minor when the unapproved change(s) in previously approved research activities, implemented without IRB approval, do not adversely affect subjects or the integrity of the study data.	Sites are to report cumulative events to AE Coordinator at time of continuing review.
Protocol violation	An incident involving an intentional deviation from the IRB-approved protocol that was not implemented in response to an emergency situation and that may impact a subject's rights, safety, and/or welfare, makes a substantial alteration to risks to subjects, or affects the scientific design of the study and/or the integrity of the resultant data. Violations may also be repeated deviations (major or minor) of the same nature. Violations can represent serious or continuing non-compliance with the federal regulations and guidelines for ethical conduct of human subject research.	Treat as an Unanticipated Problem (above)
Protocol Exceptions	A protocol exception is an IRB-approved deviation for a single subject or a small	Protocol exceptions must be approved by local IRB prior to implementation.

	group of subjects, but is not a permanent revision to the research protocol.	
--	--	--

14.7 Safety Oversight

After 15 subjects have been recruited, the study data will be reviewed by an independent anesthesiologist, blinded to study arm assignment, to ensure that no safety concerns exist. In the unlikely event that there is a safety concern, study recruitment will be halted and an independent Data Safety Monitoring Committee (DSMC), consisting of a minimum of three qualified practitioners, will be convened to evaluate the safety concern and make recommendations regarding changes to the study methods or termination of the study.

Provided that no safety concerns exist after 10 patients, the independent anesthesiologist will periodically monitor the data through the end of the study.

